To add to the challenges of diuretics and renal function, other commonly utilized measures of successful diuresis are inadequate. For example, studies suggest that daily weight and net fluid loss poorly correlate with symptom relief in ADHF. (7) Laboratory tests demonstrating hemo-concentration, increasing BUN, and increasing creatinine have been proposed as positive prognostic indicators in patients receiving IV diuretic therapy (8, 9) but these methods suffer from inadequate predictive value. Despite the considerable deficits in these techniques for monitoring diuretic use in ADHF, they continue to be used by clinicians. This has led to the unmet need to develop and utilize novel bedside monitoring to improve outcomes for patients who are receiving diuretic therapy for ADHF.

Point of care Ultrasound (POCUS) has the potential to fill this unmet need. POCUS provides clinicians with immediate diagnostic information obtained and interpreted at bedside that can augment and enhance the physical examination. Numerous studies have examined POCUS assessment of pulmonary edema and measurement of the Inferior Vena Cava (IVC) to estimate hemodynamic parameters for patients with acute decompensated heart failure (ADHF). Studies show that IVC diameter and variation in diameter during respiratory cycles correlate with right atrial pressures and can aid in the initial diagnosis of ADHF. Measurement of the IVC with POCUS correlates with prognosis and have been found to identify individuals who are at risk of being readmitted to the hospital. (10-15)

POCUS of the lung is a reliable and accurate diagnostic modality that is both sensitive and specific for pulmonary edema due to ADHF. (16, 17) Identification of interstitial syndrome, which is defined as the presence of multiple, diffuse and bilateral B-line artifacts can help differentiate pulmonary edema from other causes of dyspnea and hypoxemia in ADHF patients. Resolution of interstitial syndrome has been shown to better correlate with relief of symptoms in real time, and correlates to decrease in brain natriuretic peptide level in patients with ADHF compared to other methods. (18-24)

The 2013 American Heart Association and American College of Cardiology Foundation guidelines for heart failure management recommend diuretic therapy for patients that are admitted to hospital for ADHF and the use of intravenous (IV) diuretic therapy is a cornerstone of inpatient therapy. Monitoring with serum renal function tests and clinical assessment is also recommended. However, current guidelines do not address the use of Point of Care Ultrasound (POCUS) for the monitoring of patients admitted for ADHF. (25)

Combining serial examination of IVC and lung ultrasound in patients hospitalized with ADHF and correlating with relief of symptoms based on a standardized ADHF congestion score may be a novel approach to guide diuretic therapy and aid in monitoring and predicting improved outcomes. (26)

Despite abundance of data in use of POCUS as an initial diagnostic modality and possible treatment tool for ADHF, there is no study to date that has validated the longitudinal use

of POCUS to guide intravenous diuretic therapy. In this study we propose to examine use of serial POCUS on ADHF and its effect on the rate of worsening renal function, length of stay and rehospitalization rates in hospitalized patients.

Hypothesis:

The use of POCUS for serial assessment of volume status with IVC measurement and lung ultrasound evaluation for interstitial syndrome reduces incidence of WRF attributed to diuretic administration in patients admitted for ADHF as compared to usual care.

Specific Aims:

The overall guiding aim for our project is to determine the effectiveness of POCUS assessment in improving clinical outcomes in our patients admitted with ADHF.

To test our hypothesis, we will conduct our experiment with the following specific aims:

Primary aim: To determine if bedside written assessments of IVC and interstitial syndrome with POCUS provided to clinicians caring for patients admitted for ADHF improves outcomes compared to usual care as demonstrated by decrease in incidence of WRF while inpatient.

Secondary aim: To determine if bedside written assessments of IVC and interstitial syndrome with POCUS provided to clinicians caring for patients admitted for ADHF improves outcomes compared to usual care as demonstrated by decreased length of stay and decreased 30-day readmission rates.

Study Design

Randomized control trial open label study

Study Population

Patients admitted to Riverside University Health Systems Medical Center, a tertiary care center located in Moreno Valley, CA. Our patient population is predominately residents of Riverside and San Bernardino counties. These patients are most often lower socioeconomic status with little access to healthcare resources. Our population selected is greater than 18 years old admitted with acute heart failure exacerbation as primary admission diagnosis from Emergency department to the general internal medicine service.

Inclusion Criteria

Age >18 admitted for acute decompensated heart failure exacerbation as primary admission diagnosis from Emergency department to General Medicine ward that are administered diuretic therapy expected to be admitted for two days or more.

Exclusion Criteria

- 1) Decline consent for study
- 2) If admitted and research team not available for consent and initial evaluation prior within 6 hours of first diuretic administration
- 3) Patients in whom diuretics will not be utilized (i.e. anuric, ESRD on HD)
- 4) Inability to assess IVC (surgical anatomy, body habitus, Ileus, etc.)
- 5) Patients admitted to ICU
- 6) Patients currently on positive pressure ventilation (BiPAP)
- 7) Patients discharged from the emergency department
- 8) Patients discharged prior to evaluation by the POCUS team

Human Subjects Protection

The risk of ultrasound to for study purposes was determined to be non-significant based on the opinion of facility experts and ultrasounds history as a diagnostic modality prior to study design. This study will be submitted to the RUHS-IRB for review and approval prior to patient enrollment. After approval, informed written consent will be obtained from each research subject or their surrogate per local federal, state and county regulations. Research data will be collected and stored electronically for this study. The collected data will be entered into a data collection sheet which will be a password protected EXCEL spreadsheet and stored in the RUHS server under additional password protection. Unique identifiers will be removed from the data collection sheet and each subject assigned a random number. This number will serve to link the identity to the subject as a data linkage log. The subject identity will be kept in a separate EXCEL case book under a different password. Access to the subject information will be limited to the PI, sub PI and RUHS IRB.

Subject Recruitment

Subjects will be recruited while in the RUHS Emergency Department or RUHS Medicine ward by the PI, SubPI and Collaborators. Consent will be obtained in the RUHS Emergency Department or RUHS medicine ward by the PI, SubPI and collaborators with clinical privileges at RUHS. Resident physicians obtaining consent for the study will do so under the direct supervision of PI, SubPI and collaborators with clinical privileges at RUHS. Further, the PI will meet with Emergency and Internal Medicine Hospitalist Staff and inform them of the study. Any potential subjects will be reported to and screened for inclusion by the PI and SubPI.

Sample Size

Literature review was conducted with regard data for the incidence of worsening renal failure in patients with acute decompensated heart failure. Incidence of WRF in patients admitted for ADHF was as high as 20-40% (2-5) based on our review. Assuming an incidence of worsening renal failure of 30% in the control group, an alpha equal to 0.05 and a beta of 0.20, to detect a 25% reduction in worsening renal failure (or a 23% incidence of worsening renal failure in the intervention group), our study will require a sample size of 129 patients in each arm. To account for patients lost to follow up, who

choose to withdraw or may have an alternative diagnosis to ADHF proposed we plan to enroll up to 200 patients per arm in our study.

Methodology:

Emergency physicians and house staff will determine the diagnosis of ADHF exacerbation based on history, clinical exam, elevated BNP levels, radiology and bedside POCUS evaluation. Prior to diuretic administration patients will be screened for inclusion or exclusion in the study by checklist. If the patient or their surrogate decision maker consents to the study, they will then be randomized by random number generator to usual care or POCUS experimental arms. The POCUS team members in the ED will evaluate these patients and obtain baseline POCUS measurements.

Baseline characteristics of sex, age, body mass index (BMI), new york heart association (NYHA) heart failure Class and stage, etiology of heart failure, ejection fraction, presence of diastolic dysfunction, diabetes mellitus, hypertension, chronic kidney disease and stage, home diuretic regimen, home ACEi, home ARB, IV contrast administration, guideline directed medical therapy (GDMT) for heart failure and antibiotic (piperacillin-tazobactam, Vancomycin, Aminoglycosides) administration will be recorded for patients enrolled.

POCUS team consists of attending physicians, resident physicians and medical students. POCUS team members undergo formal training, by facility experts, for IVC assessment and B-line identification. Training for POCUS team members consists of 2 hours of classroom didactics followed by bedside teaching of standardized patients and technical skills training. Team members who collect data will be subjected to multiple choice examination with 25 standard images. Individuals certified to collect data must pass standard image exam with 95% result on two attempts. Individuals who do not pass will be directed to retake didactic and hands on sessions and then allowed to retake this examination.

In addition to their initial POCUS evaluation patients in the experimental group will immediately have a protocol-based evaluation (checklist) for interstitial syndrome (b-lines) and IVC evaluation by POCUS team. These examinations take place daily in the morning at 6am before the primary team rounds on their patient and findings are reported directly to the primary team via copy of the data sheets and verbal/written interpretation of exam results. Thoracic ultrasound examination will be performed with a Philips Sparq or Philips Lumify device with a C6-2 or C5-2 Curvilinear probe set to 15cm depth with a frequency of 48Hz. Ultrasound of the chest will be conducted on 4 regions of each lung bilaterally per international chest consensus guidelines from 2012. Positive exam is denoted by the presence of greater than three b-line artifacts in the intercostal space bilaterally, confluent B line artifact bilaterally or bilateral pleural effusions. Cardiac and subsequent IVC measurement will be conducted with a C6-2 or C5-2 curvilinear probe set to 15cm depth with a frequency of 48Hz in the subcostal view. **IVC measurement will be conducted per American society for echocardiography guidelines for assessment of the**

right heart. Either sagittal or transverse views will be obtained and IVC will be measured for collapsing with sniff maneuver.

Data scoring sheet will reflect anatomic regions of findings in binary yes/no answers. Interpretation of data on volume status will be indicated at the bottom of data sheets as high dose diuretic tolerant, high dose diuretic intolerant or consider alternative diagnosis with disclaimer.

Patients in each arm will be monitored with daily diuretic administration with dosing, intake and output, daily weight measurements and serum electrolyte levels. Additionally, patients in both arms will be monitored for ACEi/ARB prescription, hospital day of ACEi/ARB prescription, antibiotics known to cause WRF (piperacillin-tazobactam, Vancomycin, Aminoglycosides). Incidence of WRF will be monitored with daily serum creatinine levels. WRF will be defined as development of: increase in serum creatinine by ≥ 0.3 mg/dL (≥ 26.5 micromol/L) or increase in serum creatinine to ≥ 1.5 times baseline, which is known or presumed to have occurred during admission. In addition to the above variables in hospital mortality, all-cause mortality, cardiovascular mortality, length of stay in hospital days and readmission to hospital within 30 days for the same diagnosis related group (e.g. Heart failure exacerbation, heart failure or ADHF) will be recorded. Data will be exported to an excel spreadsheet and the research team with statistician will perform descriptive and quantitative analysis.

The choice of diuretic, dose and timing of administration will be left to the discretion of the primary physician. The control group will consist of patients receiving usual care for ADHF +/- bedside ultrasound assessment, with ultrasound assessment being performed at the primary physician discretion.

Data analysis

Baseline variables will be compared using descriptive statistics (e.g. chi-square for nominal data and t-test for continuous data). A multiple logistic regression will be performed for the primary study outcome (presence or absence of worsening renal failure) as well as the secondary outcome of hospital readmission within 30 days. A multiple linear regression will assess the secondary outcome of hospital length of stay.

Data safety and monitoring

Training in the pertinent diagnostic ultrasound techniques will be conducted for all individuals who collect data on the team. This training process is composed of bedside verification of skills, classroom didactics and online instructional videos. Certification to collect data will be granted to team members after passing an examination with standard images and bedside assessment by core investigators. This is a training program developed by the PI and faculty members based on clinical experience in ultrasound and clinical teaching.

The data examining training and competency for POCUS are heterogeneous with many studies examining learners of various levels and several modalities. Both individual

studies and systematic review support the use of classroom didactics with standard imaging and competency testing. Further, there is evidence to suggest excellent interrater agreement for B-lines utilizing the approach outlined (27, 28).

Incidental findings will be reported to primary team immediately and verification for these findings. Interim data analysis will be conducted by PI and collaborators every 6 months.

Funding

No funding for this study at this time

Conflict of Interest Disclosure

The authors declare that there is no conflict of interest regarding the publication of this paper.

References:

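### The stated 129 patients per arm gives about 25% power (two-sided 5%), not 80%, for the stated fall in WRF from 30% to 23%; the ceiling of 200 per arm gives about 35%

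*Protocol*

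**What the plan says.** The Sample Size section sets out the whole calculation in one sentence of the protocol:

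- Control rate: "Assuming an incidence of worsening renal failure of 30% in the control group".
- Error rates: "an alpha equal to 0.05 and a beta of 0.20". It does not say whether the test is one- or two-sided.
- Target: "to detect a 25% reduction in worsening renal failure (or a 23% incidence of worsening renal failure in the intervention group".
- Result: "our study will require a sample size of 129 patients in each arm".

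To cover loss to follow-up, withdrawal and changed diagnoses, it adds: "we plan to enroll up to 200 patients per arm in our study". No attrition rate is given.

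The Data analysis section names the test for this outcome: "A multiple logistic regression will be performed for the primary study outcome (presence or absence of worsening renal failure". WRF is the only outcome in the Hypothesis and in the primary aim.

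**The concern.** A 7-point difference between two rates in the 20–30% range usually takes several hundred patients per arm to detect with 80% power, so 129 looked far too small.

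The power claimed for the sole primary outcome is at stake. If the true figure is near one in four, a real effect of the planned size would most likely be missed. A reader relying on the stated beta of 0.20 could then take the null result as evidence that serial POCUS does not reduce WRF. Anyone judging the design's justification, including the ethics board, would also be relying on a power it does not have.

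**Working it through.** **Inputs** (all from Sample Size): p1 = 0.30; p2 = 0.23, or 0.225 for an exact 25% relative reduction (0.75 × 0.30); alpha 0.05; power 0.80; equal arms. Two-sided testing is my assumption; one-sided is shown as well.

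**1. Attempt to reproduce 129.** Pooled-variance formula, with p̄ = (p1 + p2)/2:

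n per arm = [ z(α)·√(2p̄(1−p̄)) + z(β)·√(p1(1−p1) + p2(1−p2)) ]² / (p1 − p2)²

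For 0.30 versus 0.23, p̄ = 0.265:
- first term: 1.960 × √(2 × 0.265 × 0.735) = 1.960 × 0.6241 = 1.2233
- second term: 0.8416 × √(0.2100 + 0.1771) = 0.8416 × 0.6222 = 0.5236
- n = (1.7469 / 0.07)² = 622.8, so **623 per arm**

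Other readings of the same inputs:

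| Reading | n per arm, p2 = 23% | n per arm, p2 = 22.5% |
|---|---|---|
| Two-sided, pooled | 623 | 540 |
| Two-sided, continuity-corrected | 652 | 566 |
| Two-sided, unpooled | 621 | 537 |
| Two-sided, arcsine | 622 | 538 |
| One-sided, pooled | 491 | 425 |
| One-sided, continuity-corrected | 519 | 451 |

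Misreadings do not give 129 either. A one-sample test against a fixed 30% needs 217 to 321. A 25-point absolute fall (30% to 5%) needs 36, or 43 with continuity correction. Exchanging power and beta (power 0.20) gives 45 to 100. The stated figure is not reproduced.

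**2. Power with the planned numbers.** Solving the same formula for power:

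power = Φ{ [ (p1 − p2)·√n − z(α)·√(2p̄(1−p̄)) ] / √(p1(1−p1) + p2(1−p2)) }

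For 0.30 versus 0.23, two-sided:
- n = 129: (0.07 × 11.358 − 1.2233)/0.6222 = −0.688, so power is **24.6%**
- n = 200: (0.07 × 14.142 − 1.2233)/0.6222 = −0.375, so power is **35.4%**

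Exact binomial enumeration of the uncorrected chi-square test gives 25.0% and 35.5%, so the approximation is sound.

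| Reading | Power at 129 per arm | Power at 200 per arm |
|---|---|---|
| 23%, two-sided | 24.6% | 35.4% |
| 22.5%, two-sided | 27.7% | 39.9% |
| 23%, one-sided | 35.5% | 47.7% |
| 22.5%, one-sided | 39.1% | 52.4% |

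The 200-per-arm column assumes every enrolled patient is evaluable. Going from 200 to 129 is an allowance of 71/200 = 35.5%, so at 23% two-sided the realised power lies between about 25% and 35%, depending on losses.

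**3. What these numbers can detect.** Setting power to 0.80 (two-sided) and solving for p2 with p1 = 0.30:
- 129 per arm: p2 ≈ 15.4%, a relative reduction of about 49%
- 200 per arm: p2 ≈ 18.1%, a relative reduction of about 40%

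**4. Precision.** Expected 95% CI half-width for the risk difference = 1.96 × √[(0.2100 + 0.1771)/n]:
- 129 per arm: 10.7 points
- 200 per arm: 8.6 points

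Both exceed the 7-point target.

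**The case against.** Nothing elsewhere in the protocol repairs the calculation. The fair points on the other side are these.

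- **Sidedness is not stated, and the hypothesis is directional.** This stands, so 25% and 35% rest on the two-sided assumption. The documents support a range of 25% to 39% at 129 per arm and 35% to 52% at 200. No value in it is near 80%.
- **A non-significant result is not always the likelier one.** In the single most favourable case (one-sided, 22.5%, all 200 evaluable) power is 52%. In every other case examined it is below one half.
- **Covariate adjustment in the logistic regression may change power.** It may do so somewhat, but the protocol claims no gain, and it could not plausibly close a gap of 3.3-fold (425/129) to 4.8-fold (623/129).
- **The control rate could differ from 30%.** The text fixes 30%. Across its quoted range of 20–40%, a 25% relative reduction would need 906 per arm from 20% and 356 from 40%, both two-sided.
- **It is unclear which number is wrong.** This stands. A control rate of 40% against 23%, two-sided with continuity correction, gives 128 per arm. A fall from 30% to 15% gives 121, or 134 with continuity correction. Either might lie behind 129, but both are guesses, and nothing in the protocol says that a halving of WRF is expected. The correction should not present such an effect as the intended target.

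**Conclusion.** The concern holds. The protocol's own inputs require 623 patients per arm (two-sided, pooled formula), not 129, and at least 425 under the most lenient two-arm reading. Two-sided power for the stated target is 24.6% at 129 per arm and 35.4% at 200 per arm without losses, against a claimed 80%. These figures assume equal arms, the stated 30% and 23%, and an unadjusted comparison of two proportions. The conclusion does not depend on sidedness, on rounding 22.5% to 23%, or on the formula chosen. It must be corrected because it misstates the power for the only primary outcome.

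**What to change.** Rewrite the Sample Size paragraph so that inputs, sample size and power agree, and state the sidedness of the test.

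If enrolment stays as planned:
- Delete the claim that 129 per arm detects a 25% reduction with beta 0.20.
- State that, two-sided at 5%, power for 30% versus 23% is about 25% with 129 evaluable patients per arm and about 35% with 200 evaluable per arm.
- State that, at a 30% control rate, 80% power is reached only for a fall to about 15.4% (129 per arm) or about 18.1% (200 per arm), and present these as what the design can detect, not as the expected effect.

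This costs wording only, and a less favourable stated power; no patients are added. The alternative is to keep the 25% reduction at 80% power and raise the sample size to about 623 evaluable per arm (540 if the target is 22.5%), which is a different scale of trial. If the sponsor finds that an input was mistyped, the corrected input and its recalculation should replace the present text.

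I would add one sentence: the primary result will also be given as a risk difference with 95% CI beside the logistic regression estimate, and a non-significant result whose interval includes a 7-point reduction will be called inconclusive. This is advisable but separate from the arithmetic correction.

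### The Methodology randomises before the POCUS team's baseline evaluation, but exclusions 2, 4 and 8 depend on that evaluation, so some eligibility decisions can fall after open-label allocation

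*Protocol*

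**What the plan says.** The Protocol's Study Design section describes a randomised, open-label trial. Its Methodology section first has emergency physicians and house staff make the diagnosis, partly from imaging, and then screens patients: "radiology and bedside POCUS evaluation. Prior to diuretic administration patients will be screened for inclusion or exclusion in the study by checklist". Patients who consent, or whose surrogates consent, are to "then be randomized by random number generator to usual care or POCUS experimental arms. The POCUS team members in the ED will evaluate these patients". The purpose of that evaluation is a baseline: "The POCUS team members in the ED will evaluate these patients and obtain baseline POCUS measurements". The sentence is not limited to one arm, and the later text describes the experimental group's scans as additional to an initial evaluation. The baseline scan is therefore planned for both arms.

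Three items under Exclusion Criteria refer to the same step or to what it shows:

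- Exclusion 8: "Patients discharged prior to evaluation by the POCUS team".
- Exclusion 4: "Inability to assess IVC (surgical anatomy, body habitus, Ileus, etc", among other causes.
- Exclusion 2, which applies when the patient is admitted and "research team not available for consent and initial evaluation prior within 6 hours of first diuretic administration".

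The Inclusion Criteria add that patients must be "expected to be admitted for two days or more".

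**The concern.** An eligibility criterion protects the comparison only if it is settled before allocation is known. Here the Methodology places the evaluation after the draw, while the Exclusion Criteria use it to decide who is in the trial. Someone who knows the arm could then be deciding whether a scan was adequate, whether the IVC counted as unassessable, or whether a patient who went home early had been evaluated. Such decisions need not be deliberate to differ between arms. The same decisions made before the random draw cannot be influenced by it.

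**Working it through.** The core of this point is the order of steps, so the two sections are set side by side.

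**Order in Methodology:** (1) diagnosis of ADHF, with bedside ultrasound as one input; (2) checklist screening; (3) consent; (4) random number; (5) POCUS team evaluation and baseline measurements.

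**When each exclusion can be known under that order:**

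- *Exclusion 8.* It needs to be known whether the patient left before step 5. For a consented and randomised patient, that is known only after step 4. Exclusion 7 already covers discharge from the emergency department, so exclusion 8 must reach further than that.
- *Exclusion 4.* Surgical anatomy or body habitus will often be apparent at step 2, and the diagnostic scan at step 1 may reveal others. What remains are patients in whom the difficulty first appears at step 5.
- *Exclusion 2.* It joins consent (step 3) and initial evaluation (step 5) in one entry condition. The consent half is known before the draw. The evaluation half is not, unless the evaluation comes first. This criterion therefore points to the opposite order from the Methodology.

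The two sections thus disagree on whether the initial evaluation belongs to eligibility or follows allocation.

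**Scale per patient.** Inputs: 30% control incidence of worsening renal failure and enrolment of up to 200 per arm, both from Sample Size.

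- Expected events: 0.30 × 200 = 60.
- One patient removed who would have had the event: (60 − 1)/199 = 29.65%, a shift of −0.35 points.
- One patient removed who would not: 60/199 = 30.15%, a shift of +0.15 points.
- The planned difference is 30% − 23% = 7 points, so the larger shift is 0.35/7, or about 5% of it.

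A similar exclusion in the other arm offsets the shift. The protocol does not say how many such exclusions to expect, how they would split between arms, or what risk those patients carry. The arithmetic therefore stops at one patient.

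**The case against.** The best case against has three parts.

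First, the order is inferred. The Methodology ties randomisation to consent with an explicit time word, but the sentence on the POCUS team's evaluation carries none, and exclusion 2 suggests the evaluation comes first. That is fair. Still, the sentence follows the one on randomisation and refers back to the patients just described, so evaluation after allocation is the natural reading. If the other order was intended, the text needs the same correction.

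Second, the checklist precedes consent and allocation, and exclusion 8 may be meant only for patients who left before the team reached them at all. That is possible, but the criterion does not say so.

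Third, the numbers are likely to be small. Most examples under exclusion 4 can be seen clinically, ultrasound already informs the diagnosis, an expected stay of at least two days makes early discharge uncommon, and the criteria apply to both arms. All of this stands and limits the weight of the point. Coverage of both arms does not remove it, because each case could still be judged with the arm known.

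Two stronger readings are tempting and are not supported. A reader might infer that the protocol directs removal of randomised patients, or that the result would be tilted towards POCUS. No section orders such removal, and nothing fixes a direction. A reader might also take the enrolment allowance for patients who "may have an alternative diagnosis to ADHF proposed we plan to enroll up to 200 patients per arm" as a plan to drop those patients from the comparison. The sentence gives a reason for enrolling more and orders no removal. How such patients are analysed may be set out in a statistical analysis plan that is not at hand.

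**Conclusion.** The point holds as a conflict in stated text about when eligibility is settled. It is firmest for exclusion 8, holds for the evaluation half of exclusion 2, and holds for exclusion 4 only where the cause was not evident at screening. It rests on reading the Methodology's sentences in procedural order and on the open-label design. The likely number of patients is small, and no size or direction of bias is claimed. The bound of 0.35 points is for one unmatched exclusion from one arm at 30% and 200 per arm; with fewer patients per arm it would be somewhat larger. The timing of eligibility relative to allocation is a protocol matter, so a separate analysis plan would not resolve the conflict. This is a modest weakness that is cheap to close.

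**What to change.** Reconcile Methodology with Exclusion Criteria by stating one order: checklist screening, consent, baseline POCUS evaluation in all consenting patients, exclusions 2, 4 and 8 settled and recorded, and only then the random number. Add that no patient is excluded under these three criteria after the draw.

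The change re-orders steps already in the protocol. The baseline scan is planned for both arms, and exclusion 2 already requires the team to be present for consent and initial evaluation in the same window, so no new visit is needed. The downside is that some baseline scans will be done on patients who are then not randomised.

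### The WRF rule uses an unnamed baseline, starts at admission instead of randomisation, and admits rises whose timing is only presumed, in an open-label trial

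*Protocol*

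**What the plan says.** The protocol's Methodology section gives two alternative criteria for WRF. The first is a rise in serum creatinine of at least 0.3 mg/dL, with neither a reference value nor a time interval. The second is an "increase in serum creatinine to ≥ 1.5 times baseline, which is known or presumed to have occurred during admission". The closing clause on timing can be read as covering both criteria.

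On measurement, the same section says "Incidence of WRF will be monitored with daily serum creatinine levels". It does not say which draw is the reference. The list of baseline characteristics contains "chronic kidney disease and stage, home diuretic regimen, home ACEi, home ARB, IV contrast administration" among other items, but no serum creatinine.

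Randomisation comes after consent (Methodology). Subject Recruitment says "Consent will be obtained in the RUHS Emergency Department or RUHS medicine ward". Neither section ties randomisation to a blood draw.

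Study Design describes a "Randomized control trial open label study". No blinded assessor or adjudication of WRF is described. The research team and a statistician analyse the data (Methodology), and the principal investigator and collaborators run interim analyses every six months (Data safety and monitoring).

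**The concern.** Three things decide whether a patient has the primary event, and the rule leaves each of them open.

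- **The reference.** A patient whose creatinine falls after admission and then climbs back by 0.3 mg/dL to about its starting level has an event if measured from the lowest value, and none if measured from the first.
- **The start of the window.** The rule counts from admission. Any rise between admission and randomisation is eligible, although the allocated strategy had not begun.
- **The timing call.** A rise may be counted because someone presumes when it happened. No rule says when that is allowed or who decides.

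Events that precede randomisation should be balanced between arms in expectation, so they dilute the treatment effect. The timing call is different. If it is made with the arm known, it can move the result in either direction.

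**Working it through.** **1. The plan's own figures.** Sample Size assumes 30% WRF in control and a 25% relative reduction: 0.30 × 0.75 = 0.225, which the protocol gives as 23%. The working contrast is 30% versus 23%, a difference of 7.0 points and a relative risk of 0.23/0.30 = 0.767.

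**2. The definition against the sequence of events.**

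| Element | What the rule needs | What the protocol gives |
|---|---|---|
| Reference for the 0.3 mg/dL criterion | A named value | None |
| Reference for the 1.5-times criterion | A named value | A baseline tied to no sample |
| Start of window | Randomisation | Admission |
| Timing of the rise | Observed | Observed or presumed |
| Scorer | Formula, or blind to arm | Not described; open label |

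**3. Dilution, equal in both arms.** Assume a share p of each arm is scored as WRF for a rise that precedes randomisation, and the rest follow 30% versus 23%. The observed risk is p + (1 − p) × r. The documents give no value for p, so 5 to 15% is an illustrative range.

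| p | Control | POCUS | Difference (points) | Relative risk |
|---|---|---|---|---|
| 0 | 30.0% | 23.0% | 7.00 | 0.767 |
| 5% | 0.05 + 0.95 × 0.30 = 33.5% | 0.05 + 0.95 × 0.23 = 26.85% | 6.65 | 0.801 |
| 10% | 37.0% | 30.7% | 6.30 | 0.830 |
| 15% | 40.5% | 34.55% | 5.95 | 0.853 |

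**4. Scoring that differs by arm.** Let d be the share of patients whose status is debatable, and let s₁ and s₀ be the probabilities that such a patient is scored as an event in each arm. The bias in the risk difference is d × (s₁ − s₀), which is at most d. With d = 3 to 5%, the ceiling is 3 to 5 points. It is reached only if every debatable patient is an event in one arm and none is in the other. If the scoring probabilities differ by 50 percentage points, the bias is 0.5 × 3 = 1.5 to 0.5 × 5 = 2.5 points.

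To see what a net excess e in control does when there is no true effect (30% in both arms), take a = 0.30 + e, b = 0.30 and p̄ = (a + b)/2. Let SE₀ = √(2p̄(1 − p̄)/n) and SE₁ = √((a(1 − a) + b(1 − b))/n). The chance of a significant two-sided result is 1 − Φ((1.96·SE₀ − e)/SE₁) + Φ((−1.96·SE₀ − e)/SE₁).

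| Net excess e | 129 per arm | 200 per arm |
|---|---|---|
| 2 points | 6.4% | 7.2% |
| 3 points | 8.1% | 9.9% |
| 5 points | 13.7% | 18.7% |

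The arm sizes are the protocol's stated requirement and its planned maximum, taken as given. Whether they follow from the stated inputs is a separate question on which this point does not depend.

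**The case against.** The strongest reply is that the words already shut out most of what one might fear. A reader might infer that kidney injury present on arrival will be scored as WRF. For example, a clinic value of 1.1 and an emergency department value of 1.8 mg/dL give 1.8/1.1 = 1.64 times the older value. The documents do not support that inference. The definition asks for a rise that develops during admission, the primary aim speaks of the inpatient stay, and the hypothesis concerns WRF attributed to diuretics. Outpatient values are never mentioned. A missed daily draw could equally leave timing to be presumed, so that clause does not imply an outpatient reference.

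A reader might also take the exclusion "If admitted and research team not available for consent and initial evaluation prior within 6 hours of first diuretic administration" to mean that the reference creatinine may follow the first diuretic dose. That criterion governs consent and evaluation, not blood draws, and Methodology places screening before diuretics. If anything, a six-hour limit suggests that the interval between first treatment and randomisation is often short, which would keep that route small.

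Two further points stand. Creatinine is a laboratory value, so knowledge of the arm matters only where the reference or the timing is in dispute. And a statistical analysis plan, not shown here, might name the baseline sample.

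What survives is narrower but real. The presumption clause and the admission window stand in the protocol's own definition of the primary outcome, and a later plan could repair them only by departing from it.

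**Conclusion.** The point holds in limited form. The defect is confined to the choice of reference value, the interval from admission to randomisation, and rises of presumed timing. Within those limits, the rule can count events that POCUS could not have prevented, and it leaves some calls to people who may know the arm. That they would know it is inferred from the open-label design and the absence of any described blinded scoring.

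The size cannot be determined from the documents. If 5 to 15% of both arms were affected equally, the 7.0-point difference would shrink to between 6.65 and 5.95 points, which is modest. A reader might infer a bias of 3 to 5 points against the 7-point target. That is a ceiling for an assumed 3 to 5% of debatable patients all scored in opposite ways by arm, and nothing in the documents says this would happen. Should-fix, with moderate confidence.

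**What to change.** Amend the WRF definition in Methodology as follows.

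1. For both criteria, define baseline as the last serum creatinine drawn before randomisation, wherever it was drawn, and record the time of the draw.
2. Delete the clause that accepts a known or presumed rise during admission.
3. Count only rises seen in samples drawn after randomisation and up to discharge.
4. Derive the event by formula from the laboratory values, with no judgement.
5. State in advance how a patient without a pre-randomisation value is handled.

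The cost is protocol wording and a spreadsheet formula. There are two downsides. The counted WRF incidence may be somewhat lower than under the present rule. The plan must also confirm that a creatinine before randomisation is available for every patient, because the protocol does not say that one is drawn.
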